2. Ensure that the study is not commenced until all necessary approvals have been obtained.
3. Ensure that a written informed consent is obtained from each subject prior to any data collection using the most recent IRB/EC approved subject Informed Consent Form (ICF).
4. Provide all required data and reports, as well as agree to allow source document verification of study data with subject’s medical records by a BionX, designee and/or any regulatory authorities.
5. Allow BionX personnel or its designees, as well as regulatory representatives, to inspect and copy any documents pertaining to this clinical investigation according to the federal, state, and institutional data and privacy protection laws.

Investigator Signature

I have read and understand the contents of the study and agree to abide by the requirements set forth in this document.

Investigator Name (print)

Study Center (print)

Investigator Signature

Date

Protocol Synopsis

EmPOWERing Active Seniors with Energy

| | |
|---------------------------------------|--|
| Study Population | The study population will include up to ten (10) unilateral transtibial amputees. |
| Intended Use | The device is intended to replace a missing foot and ankle. The emPOWER Ankle is to be used exclusively for fittings of lower-extremity amputations as prescribed by a healthcare professional. |
| Control | Subjects serve as their own control with assessments using their prescribed passive lower-extremity prosthesis at Baseline and after 2 weeks of re-accommodation after 3 months of use of emPOWER. |
| Study Design | This is a pilot, prospective, cross-over, open label observational study. Phase I: Screening through 3 Months Phase II: Long-term follow-up of subjects using the emPOWER Ankle in their daily lives from 3 Months through 12 Months |
| Primary Objective | The primary objective of this study is to characterize the increase in the distance subjects can walk during a six (6) minute period while wearing the emPOWER Ankle compared to a passive lower-extremity prosthesis. |
| Primary Effectiveness Endpoint | The primary endpoint of this study will be an improvement in walking distance with the emPOWER Ankle compared to the distance walked with the subject’s passive prosthesis as shown by 6 minute Walk Test (6MWT) results at 3 months. |
| Secondary Endpoints | The secondary endpoints of this study will compare the following assessments on the emPOWER Ankle to the subject’s passive prosthesis at Baseline (before wearing the emPOWER, when available) and Crossover: 
 • 12 minute Walk Test (12MWT) • 10 meter Walk Test (10MWT) • L-Test for overall mobility and fall risk • Time and Quality of Ramp Ascent • Time and Quality of Ramp Descent • Activities-specific Balance Confidence (ABC) Scale • Falls Efficacy Scale • Amputee Mobility Predictor (AMP) Assessment • Prosthetic Limb Users Survey of Mobility (PLUS-M) (12 item Short Form) • Patient-specific Functional Scale (PSFS) • Numeric Pain Rating Scale (NPRS) • Activity monitoring over two weeks prior to the assessment session |

| | |
|--|--|
| | 
with the emPOWER Ankle and the re-assessment session with the previous foot using a Fitbit monitor.
 
 • Falls: Diary of reported falls for two weeks • Activity Diary to allow for self-reporting of activities of daily living and unique user experiences with the emPOWER Ankle for two weeks • PROMIS Physical Function (Custom) • PROMIS Global Health Short Form • PROMIS Fatigue Short Form (7a) • PROMIS Pain Intensity Short Form (3a) 
Long-term follow-up of subjects who agree to continue wearing the emPOWER Ankle at 3, 6 and 12 months with all outcome measures (except the activity monitoring and diaries of steps, activity and falls at 6 & 12 months).
 |
| 
Number of Subjects and Number of Study Sites
 | 
Up to ten (10) subjects will be enrolled into this study at one (1) study site.
 |
| 
Study Duration
 | 
Overall study enrollment is estimated to take two (2) months. The subject's study participation duration will last approximately four (4) months for the first phase. If the subject elects to continue in the second phase, that will last for an additional 9 months.
 |
| 
Key Inclusion Criteria
 | 
 I-1. Males and females I-2. 55 years or older I-3. Subjects with transtibial amputations of either leg at least 1-year prior I-4. Suction or elevated vacuum suspension and Socket Comfort Score of at least 6 I-5. Sock fluctuation of ≤ 8 ply per day I-6. K-level rating of 3 or 4 based on the AMP Assessment Tool I-7. Ability to walk at a walking speed of > 0.75 meters per second with the current prosthesis I-8. Unilateral amputees (up to 7 bilateral amputees can be included, 1 per site in addition to the unilateral amputees who will be analyzed as a separate sub group) I-9. Foot size: 25-30 cm I-10. Ability to complete a continuous 6MWT I-11. Ability to provide written, informed consent |

| | |
|------------------------------------|--|
| | 
I-12. Ability to complete study visits and study documents
 
I-13. Ability to manage the complexity of a powered device including charging and changing batteries as needed
 
I-14. Ability to read and understand English
 |
| Key Exclusion Criteria | 
E-1. Subjects who have never used a prosthetic device
 
E-2. Less than 55 years of age
 
E-3. Weight <150 lbs. or > 287 lbs.
 
E-4. Transfemoral amputees
 
E-5. Active sores or ulceration on subject’s residual limb
 
E-6. Sore on contralateral foot
 
E-7. Cuff-link socket suspension
 
E-8. Socket Comfort Score less than 6
 
E-9. Sock fluctuation of > 8 per day
 
E-10. K level of 1 or 2
 
E-11. Amputation clearance < 8.625”
 
E-12. History of stroke or TIA that impairs current walking
 
E-13. Recent history of excessive falling defined as more than 2 falls requiring medical assistance in the prior year
 
E-14. Medications potentially affecting balance
 
E-15. Recent hospitalization (within past 3 months)
 
E-16. Cognitive deficiency that would impact ability to charge and change batteries as needed
 |
| Primary Statistical Methods | 
Subjects will be enrolled to characterize improvements with the emPOWER Ankle compared to the subject’s passive prosthesis. Data analysis will be descriptive in nature.
 |

Table 12.2.1: Adverse Event Reporting Requirements 24

Table 12.2.2: Sponsor and BionX Reports..... 25

12.3. Device deficiencies, Device failures, Malfunctions, and Product Nonconformities.. 25

12.4. Reporting to Regulatory Authorities /IRBs /ECs /Investigators 25

13. Risk Benefit Analysis..... 25

13.1. Known and Anticipated Risks 26

13.2. Risk Minimization 26

14. Subject Benefit 26

15. Ethical Considerations..... 27

15.1. Study Conduct 27

15.2. Institutional Review Board..... 27

15.3. Informed Consent Form 27

15.4. Obtaining Informed Consent 27

15.5. Amending the Protocol..... 28

15.6. Emergency Actions 28

15.7. Protocol Adherence 28

16. Study Logistics 28

16.1. Data Management..... 29

16.2. Monitoring and Auditing..... 29

16.3. Device Accountability 29

16.4. Record Retention 29

16.5. Criteria for Terminating Study 30

16.6. Criteria for Suspending/Terminating a Study Center 30

16.7. Insurance 30

16.8. Publication Policy..... 30

17. References 31

18. Appendices 33

18.1. Abbreviations 33

18.2. Patient Specific Functional Scale 33

1. Introduction

1.1. *Study Rationale*

Safety and performance of the emPOWER Ankle has been shown in a laboratory setting.

The primary objective of this study is to show increased mobility and improvement in balance and other activities of daily living with the emPOWER Ankle compared to standard carbon fiber prosthetic legs, in active seniors to support marketing and reimbursement needs.

[figure not shown]
2. Device Information

2.1. *Principle of Operation*

The emPOWER Ankle, a *Class II exempt* device (in accordance with 21 CFR 890.3500, which does not require pre-market notification per section 510(k)), represents the first significant redesign of the BiOM Ankle. The Ankle is a commercially-available prosthetic device that restores ankle power across all walking speeds [1-3]. This emulation is achieved through three technologically-novel functionalities. First, the ankle provides late-stance **powered assist** [2-4]. Second, the device provides **stiffness modulation** after heel strike, which decelerates the body and thereby reduces impact loads. Finally, the device is adjusted with **personal bionic tuning**, in which ankle stiffness and power levels are personalized for each user, enabling the user to walk within normal biologic ranges [2, 3].

The ankle optimizes ankle stiffness and power through user-specific settings using a quantitative treatment paradigm in which its dynamic response is adjusted to provide biologically-normal ankle behaviors [2, 3], removing the subjective and qualitative nature of current prosthetic user evaluations and fittings. As shown in Section 2.2, the emPOWER Ankle was designed with both passive and actively powered components in order to emulate biological function throughout the gait cycle. The device continuously modulates ankle stiffness, spring equilibrium and propulsive torque throughout a walking gait cycle [2, 5-11]. Computers and sensors that operate biomimetic control firmware guide the device's performance. The processors are able to adjust the ankle's stiffness, spring equilibria, and propulsive torque 500 times a second. Similar to the muscle-tendons and neural reflex control of the human ankle joint, the device is capable of positive torque feedback. An increase in the sensed prosthetic ankle joint torque triggers an increase in the torque generated by the actuator, resulting in the automatic modulation of ankle power assist with changes in both walking velocity and ground inclination [7,8]. During personal bionic tuning, ankle stiffness and the magnitude and timing of power assist are measured directly from sensors within the prosthesis and then adjusted to match the performance of a biological ankle. Thus, with appropriate tuning of the prosthesis, the walking gait of the user dynamically emulates the walking gait of a non-amputee user across the full range of walking velocities [1-3].

2.2. Figure: The emPOWER Ankle

3. Intended Use

The device is intended to replace a missing foot and ankle. The emPOWER Ankle is to be used exclusively for fittings of lower extremity amputations as prescribed by a healthcare professional.

4. Primary Objective

The primary objective of this study is to characterize the increase in the distance subjects can walk during a 6 minute period while wearing the emPOWER Ankle compared to a passive lower-extremity prosthesis.

5. Study Design

This is a pilot, prospective, cross-over, open label observational study. Study subjects will remain blinded to the results from their testing and questionnaires from their passive device until they have complete the study procedures for the emPOWER.

6. Study Endpoints

6.1. Primary Endpoint

The primary endpoint of this study will be an improvement in walking distance with the emPOWER Ankle compared to the distance walked with the subject’s passive prosthesis as shown by 6MWT results at 3 months.

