6.2. Secondary Endpoints

The secondary endpoints of this study will compare the following assessments on the emPOWER Ankle to the subject’s passive prosthesis at Baseline (before wearing the emPOWER, when available) and Crossover:

- 12 minute Walk Test (12MWT)
- 10 meter Walk Test (10MWT)
- L-Test for overall mobility and fall risk
- Time and Quality of Ramp Ascent
- Time and Quality of Ramp Descent
- Activities-specific Balance Confidence (ABC) Scale
- Falls Efficacy Scale
- Amputee Mobility Predictor (AMP) Assessment
- Prosthetic Limb Users Survey of Mobility (PLUS-M) (12 item Short Form)
- Patient-specific Functional Scale (PSFS)
- Numeric Pain Rating Scale (NPRS)
- Activity monitoring
- Falls
- Activity Diary
- PROMIS Physical Function (Custom)
- PROMIS Global Health Short Form
- PROMIS Fatigue Short Form (7a)
- PROMIS Pain Intensity Short Form (3a)

Long term follow-up of subjects who agree to continue wearing the emPOWER Ankle at 3, 6 and 12 months with all outcome measures (except the diaries of activity and falls at 6 & 12 months).

7. Study Population

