At the second visit, the subject will complete the following study assessments wearing the passive prosthetic:

- 6MWT
- Ramp Ascent
- Ramp Descent
- ABC Scale
- Falls Efficacy Scale
- Mobility PLUS-M (12 item Short Form)
- PROMIS Questionnaires

At the end of the second visit, subjects will be fitted with the emPOWER Ankle by a qualified clinical prosthetist, trained by BionX personnel. This fitting includes selection of the appropriate size and category carbon fiber foot, alignment, and tuning in accordance with the emPOWER Instructions For Use (IFU). The prosthetist will make a determination that the tuning was successful (within the bounds specified by the IFU) and the Investigator will maintain a copy of the Tuning Record. This initial Tuning Record may also be used to verify that the subject has the ability to walk at a self-selected walking speed (SSWS) > 0.75 meters per second with the current prosthesis and can walk with variable cadence, where variable cadence is defined as three distinguishable walking speeds with a minimum SSWS of 0.75 m/s (one below SSWS, and one above SSWS) on the Tuning record. Distinguishable will be defined as no overlap between the three (3) primary step groupings for each walking speed displayed on the Tuning Record.

At fitting of the emPOWER Ankle, the Investigator will instruct the subject to utilize the device for a 16-day period of time, within the intended and foreseeable range of use (e.g. – ramps, stairs, limited running or jumping, stepping sideways, etc.). In addition, the investigator will take the subject through a series of default operating conditions of the emPOWER Ankle in the clinic setting such as with the power turned off.

Each subject will take the emPOWER Ankle (including batteries and charger) home for 16 days (to ensure 14 full days of step counts) of use in everyday life situations. The subject will not be under the observation of the Investigator during this take home period. During the at home portion of the study, subjects will continue to monitor daily steps with use of a Fitbit® One™ during the time that they are wearing the emPOWER Ankle. Subjects will also maintain an Activities of Daily Living Diary during the take home evaluation portion of the study. This Diary will allow subjects to note specific activity changes due to the emPOWER Ankle and serve as a log for recording any falls.

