As a quality check, the steps on the emPOWER Ankle, as recorded in the emPOWER Tuning Records, will also be recorded at baseline and at follow-up.

9.6. *Phase I: 3rd Visit - emPOWER Follow Up*

After the 16-day period of use, the subject will return to the prosthetist. The window for this visit is +1 week.

During this visit, the subject will complete the following study assessments wearing the emPOWER Ankle:

- 6MWT
- Ramp Ascent
- Ramp Descent
- AMP
- ABC Scale
- Falls Efficacy Scale
- Mobility PLUS-M (12 item Short Form)
- PROMIS Questionnaires

In addition, the patient diary will be reviewed for Fitbit steps, falls and daily activity.

The Investigator will maintain a copy of the Tuning Record.

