9.7. Phase II: 4th Visit – 3 Month Visit

Subjects will be invited to participate in long-term follow-up. For a minimum of 14 days prior to this visit, the subject should wear the Fitbit and complete the patient diary for steps, fall and daily activity.

Subjects will be seen by the prosthetist after wearing the emPOWER Ankle for 3 months. The window for this visit is -1 week / + 6 weeks.

During this visit, the subject will complete the following study assessments wearing the emPOWER Ankle:

- 12MWT (with distance walked assessed at 6 and 12 minutes)
- 10MWT
- L-Test
- Ramp Ascent
- Ramp Descent
- ABC Scale
- Falls Efficacy Scale
- AMP
- Mobility PLUS-M (12 item Short Form)
- PROMIS Questionnaires
- Patient-specific Functional Scale (PSFS)
- Numeric Pain Rating Scale (NPRS)

In addition, the patient diary will be reviewed for Fitbit steps, falls and daily activity.

At the end of the study visit, subjects will return to wearing their passive prosthetic foot for 2-4 weeks of re-accommodation.

The subjects are reminded to wear the Fitbit activity monitor and complete the patient diaries to track activity, falls and self-reporting of activities of daily living.

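### The 3-month 6-minute comparison may be selected for benefit, and the earlier Visit 2/Visit 3 pair that could show this has no stated role

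*Combined protocol and SAP*

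**What the plan says.** **Primary endpoint.** Section 6.1 and the Synopsis define it as improvement in walking distance "as shown by 6MWT results at 3 months". Neither names the passive visit. The Synopsis entry for the control gives two passive assessments, baseline and after re-accommodation.

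**Secondary endpoints.** Section 6.2 lists 18 items. The 12MWT and 10MWT are among them; the 6MWT is not. The comparator is the "passive prosthesis at Baseline (before wearing the emPOWER, when available) and Crossover". A closing sentence adds "Long term follow-up of subjects who agree to continue wearing the emPOWER Ankle at 3, 6 and 12 months". Visit 3 is not mentioned.

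**Schedule.** Table 9.11.1 has the stand-alone 6MWT at Visits 2 and 3 only. At Visit 2 (Section 9.5) "the subject will complete the following study assessments wearing the passive prosthetic", with the 6MWT first in the list. For Visit 3, Section 9.6 says "After the 16-day period of use, the subject will return to the prosthetist", and the 6MWT is then done on emPOWER. From Visit 4 on, the 6-minute distance is the midpoint reading of a 12MWT.

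**Who reaches 3 months.** Section 9 follows all enrolled subjects through Visit 3 as Phase I, then offers Phase II to those who benefit. Section 9.7 heads the 3-month visit Phase II. The Synopsis instead runs Phase I to 3 months, and Sections 7.3 and 9.7 invite subjects to long-term follow-up without a benefit condition.

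**Losses.** Section 7.2 replaces only subjects withdrawn before they walk on emPOWER. No rule for missing values is given. Section 16.1 promises to report data from all subjects up to completion or withdrawal.

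**The concern.** The study asks how far a subject walks in six minutes on emPOWER compared with the passive foot. A subject who does not go on to the 3-month visit has no emPOWER value for the primary endpoint as worded. If going on depends on apparent benefit, as Section 9 says, the 3-month mean describes those who did well and can favour the device even with no average effect.

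The plan already collects a comparison that comes before this gate, the passive 6MWT at Visit 2 and the emPOWER 6MWT at Visit 3. Because no endpoint names it, whether and how it is reported is open until the data are known. That matters in an open-label study whose stated rationale (Section 1.1) includes marketing and reimbursement support.

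**Working it through.** The plan states no SD, retention rate or sample-size derivation. The one figure to reproduce is the benchmark in Section 10.2: 0.1 m/s × 360 s = 36 m, which agrees.

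**1. Where each 6-minute distance sits**

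| Visit | Device | Source of distance | Phase (Section 9 and visit headings) | Role in the endpoint text |
|---|---|---|---|---|
| 2 | passive | 6MWT | I | baseline passive comparator (no walk at Visit 1) |
| 3 | emPOWER | 6MWT | I | none named |
| 4 | emPOWER | 12MWT, 6-minute mark | II | primary |
| 5 | passive | 12MWT, 6-minute mark | II | crossover passive comparator |

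Two pairs share a test format: Visits 2/3 and Visits 4/5. Only Visits 2/3 fall before Phase II as Section 9 defines it.

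**2. Weight of one subject.** Sample size is up to 10 (Section 7.3) or 5 (Section 9). One subject without a 3-month value removes 1/10 = 10% or 1/5 = 20% of the primary data.

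**3. Selection by a benefit gate (illustration).** Assumed: measurement SD s_e = 20 m per test; SD of true benefit s_b = 20 to 40 m; true mean benefit 0; a subject continues if D = Visit 3 − Visit 2 is above 0. Half continue. With √(2/π) = 0.798 and SD(D) = √(s_b² + 2s_e²):

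- mean of Visit 4 − Visit 2 among continuers = 0.798 × (s_b² + s_e²) / SD(D)
- mean of Visit 4 − Visit 5 among continuers = 0.798 × s_b² / SD(D)

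| s_b | SD(D) | Visit 4 − Visit 2 | Visit 4 − Visit 5 |
|---|---|---|---|
| 20 m | √1200 = 34.64 | 0.798 × 800/34.64 = 18 m | 0.798 × 400/34.64 = 9 m |
| 40 m | √2400 = 48.99 | 0.798 × 2000/48.99 = 33 m | 0.798 × 1600/48.99 = 26 m |

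A simulation of one million subjects agrees (18.4 and 32.5 m; 9.2 and 26.0 m). With a true mean of 36 m, 77 to 85% continue. The simulated 3-month means are then 42 to 52 m against Visit 2, an excess of 6 to 16 m, or 39 to 49 m against Visit 5, an excess of 3 to 13 m.

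**4. Looser selection (illustration).** If a fraction p stays, and the tendency to stay correlates r with a subject's own change, the mean under no effect is r × [φ(z)/p] × SD, where z cuts off the lower 1 − p.

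- p = 0.7, r = 0.5, SD 36 m: 0.5 × 0.497 × 36 = 9 m (SD 20 to 50 m: 5.0 to 12.4 m).
- p = 0.5, r = 1, SD 36 m: 0.798 × 36 = 29 m (SD 20 to 50 m: 16 to 40 m). This is an extreme case.

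**5. What the earlier pair would show.** In the model of step 3, Visit 3 − Visit 2 averages 0 m over all subjects but 0.798 × 34.64 = 28 m to 0.798 × 48.99 = 39 m among continuers. Reporting both exposes the selection. The gap overstates the effect on the 3-month result, because part of it is Visit 3 test error that does not recur at Visit 4. The zero average assumes that everyone fitted reaches Visit 3 and that there is no practice or expectation effect.

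**6. Precision.** The 95% half-width for a paired mean is t(0.975, n−1) × SD/√n. With an assumed SD of 30 to 60 m it is 21.5 to 42.9 m for n = 10, 27.7 to 55.5 m for n = 7 and 37.2 to 74.5 m for n = 5.

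**The case against.** The strongest reply is that this is a descriptive pilot with no hypothesis test, and that the documents do not shut Visit 3 out. Several of its points stand.

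- A reader might infer that the Visit 3 walk is discarded and that subjects lost before 3 months contribute nothing. The text does not say so. The objective, the comparison in Section 10.2 and the Section 11 formula name no visit, so each could take the Visit 3 value, and Section 16.1 promises general reporting.
- A reader might infer that Visits 2/3 are the only pair using the same 6-minute test. They are not. Visits 4 and 5 both use the "12MWT (with distance walked assessed at 6 and 12 minutes", and Visit 5 is a control the Synopsis names. The same text answers any claim that no 6-minute distance exists at 3 months.
- A reader might infer that the earlier pair is free of loss. Fitted subjects go home for 16 days and can leave before Visit 3, without replacement under Section 7.2.
- The benefit gate rests on Section 9. The Synopsis runs Phase I to 3 months and gives it about four months, which would cover the 3-month visit for everyone. Sections 7.3 and 9.7 state no benefit condition.

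These points remove the claims of exclusion and uniqueness. They do not give Visit 3 a role. Nor do they secure the 3-month visit for everyone, since Section 6.2 itself puts 3 months under follow-up of subjects who agree to continue.

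**Conclusion.** The concern holds in a limited form. No endpoint names the Visit 3 emPOWER 6MWT, although with Visit 2 it is the 6-minute pair planned for every fitted subject before the Section 9 gate. The primary, read at 3 months, may be selected for benefit.

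Under a strict gate and no true effect, the illustrated bias is 18 to 33 m against Visit 2 and 9 to 26 m against Visit 5. Under looser selection it is about 9 m. The upper values approach the 36 m benchmark. All of these depend on assumed SDs, retention and correlation; none is an estimate for this study.

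It would go too far to conclude that the 3-month result is biased. The documents conflict on whether continuation depends on benefit, and without that condition selection would have to come from subjects' own choices. This is a worthwhile, cheap improvement to a descriptive plan and not a fault that defeats it.

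**What to change.** Add one supportive endpoint to Section 6.2 and the Synopsis: *Change in 6MWT distance (metres and percent), emPOWER at Visit 3 versus passive at Visit 2, in all fitted subjects with a Visit 3 test.*

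Report it beside the 3-month result, once for all such subjects and once for those who reach Visit 4, with the number missing at each visit. Label it as early (16 to 16 + 7 = 23 days), open-label, fixed-order use. Name the visits in the Section 11 formula. Reconcile Section 9, the Synopsis, Section 7.3 and Section 9.7 on where Phase I ends and who is offered Phase II.

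The cost is a line of endpoint text, a table row and the reconciliation; both walks are already scheduled. The comparison reflects only early use. It supports the 3-month primary and makes selection visible, but it neither replaces that result nor removes the selection from it.
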